Date	9/27/18
Title	Are we supporting the apex during hysterectomy for pelvic organ
	prolapse?
Principal Investigator	[name], MSc
Sub-Investigators	[name]; [name]; [name],
	MD; [name], DO; [name]
Research Specialist	[name], MS
Department	Department of OB/Gyn, Division of Urogynecology and
	Reconstructive Pelvic Surgery
Hatton #	17-091

Purpose of Study:

- To determine whether gynecologic surgeons at a large community hospital are already meeting the recently recommended best practice of supporting the vaginal apex at time of hysterectomy for pelvic organ prolapse.
 - Primary Aim: To determine the proportion of patients undergoing hysterectomy for the indication of pelvic organ prolapse having concurrent apical suspension such as: McCall's culdoplasty, Uterosacral Ligament Suspension, Sacrospinous Ligament Fixation, Abdominal Sacrocolpopexy, or Robotic Sacrocolpopexy.
 - Secondary Aims: Identify characteristics of surgeons not meeting the recommended best practice including their training, location of operation, operative times, concurrent procedures and estimated blood loss.

Hypothesis or Research Question

 We hypothesize that fewer than 10% of patients having hysterectomy for pelvic organ prolapse will not undergo concurrent apical support, being defined as McCall's Culdoplasty, Uterosacral Ligament Suspension, Sacrospinous Ligament Fixation or Robotic/Abdominal Sacrocolpopexy.

Background

The prevalence of pelvic organ prolapse (POP) in the United States is estimated to be between 40-50% with an anticipated increase over the next several decades¹⁻³. Approximately 300,000 women undergo surgeries to repair POP in the United States every year⁴. Following pelvic reconstructive surgery, recurrence rates of symptomatic prolapse range between 6-30%⁵⁻⁹. This number has changed in recent years to favor a lower recurrence rate. This change in recurrence rate may be attributed to the efforts of pelvic surgeons in restoring proper levels of support during repairs.

Our understanding of pelvic anatomy and its support has been significantly improved over recent decades, with many researchers reporting on details and mechanics previously not understood. A landmark article by DeLancey¹¹ proposed a now widely accepted model

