- o A chart review will be performed on all patients identified.

- Inclusion criteria
 - Adults 18 years of age or older
 - Underwent hysterectomy for pelvic organ prolapse, performed at a TriHealth facility between October 2012 and October 2017
- Exclusion criteria
 - Age < 18 years old
 - Pelvic Organ Prolapse was not an indication for their surgery
 - Surgery performed by a physician of Cincinnati Urogynecology Associates.
- Sample size
 - Given the retrospective nature of this study, a sample size calculation is not indicated. However, estimating the number of charts that may be available can be garnered from internal reports on department activity. Between October 2012 to October 2017, 792 hysterectomies took place at a Trihealth Facility for the indication of prolapse. Excluding those performed by a physician of the Cincinnati Urogyn Associates group, there are approximately 194 cases eligible for review. With this in mind, in order to provide for potential differences in case number during the years within the study period, we request permission to review up to 250 cases.

Data Collection

- Each chart will be reviewed and the following data will be collected or extrapolated:
 - General demographic data name, date of birth, age, race, parity, BMI
 - Select comorbidities (connective tissue disorders, history of chronic constipation, history of chronic cough)
 - Operative details Date of surgery, concurrent procedures performed, type of apical support, length of procedure, facility or location of procedure performed, estimated blood loss, reported intra-operative complications, primary surgeon, whether FPMRS or General OB/GYN.

Intervention or experimental aspect of the study

- No intervention will occur as part of this study.
- There are no potential risks to the study population by any aspect of the study.

Statistical Analysis

 Given the descriptive nature of this study, limited statistical analysis will be performed. The proportion of patients who did not have concurrent apical support procedures performed will be calculated. Furthermore, the proportion of patients who had various postoperative outcomes (as defined above) will be calculated and compared to previous published literature.

Ethical Considerations

Informed consent

 Since this is a retrospective study, waivers of Informed Consent and Authorization will be requested.

• Privacy information

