- Extensive efforts will be made to ensure and maintain participant confidentiality. All identifying information will be maintained in a secure area at all times. All communication between staff members regarding participant data will occur via the Subject ID number only. However, identifying information will be retained in the original/source documents.
- The Excel spreadsheet will be stored on a password protected, encrypted
 TriHealth computer for ten years following study closure, and then purged.

Cost/Budget

• This study will incur no cost to the institution, the participants, or the investigators.

Estimated Period of Time to Complete Study		
Estimated Period of Time to Complete Study		
When will study begin?	January 2018	
Protocol Development	2 weeks	
Completed		
Admin Review Time	2 weeks	
IRB Approval	3 weeks	
Data collection	8 weeks	
Data analysis	2 weeks	
Presentation development	2 weeks	
(if applicable)		
Manuscript Development	4 weeks	
(if applicable)		
Journal submission process	4 weeks	
(if applicable)		
Study closure	2 weeks	

• When and how will results be disseminated?

The results will be disseminated at one of our division research meetings and potentially as a presentation at a national meeting.

References

- 5. Dallenbach P. To mesh or not to mesh: a review of pelvic organ reconstructive surgery. Int J Womens Health 2015; 7:331-343

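### Route of hysterectomy is not on the data list, so operative time and blood loss for surgeons who omit apical support cannot be read within route

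*Combined protocol and SAP*

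**What the plan says.** The secondary aim, under Purpose of Study, is to "Identify characteristics of surgeons not meeting the recommended best practice including their training, location of operation, operative times, concurrent procedures and estimated blood loss". Operative time and blood loss are two of the five items it names.

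Under Data Collection, the operative details open with "Date of surgery, concurrent procedures performed, type of apical support, length of procedure, facility or location of procedure performed, estimated blood loss" and close with "reported intra-operative complications, primary surgeon, whether FPMRS or General OB/GYN". The approach used for the hysterectomy itself does not appear.

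Eligibility, under Participants, is "Underwent hysterectomy for pelvic organ prolapse, performed at a TriHealth facility between October 2012 and October 2017", with no limit on route. Approach is mentioned only for some apical procedures: the definition of support in the hypothesis ends with "Sacrospinous Ligament Fixation or Robotic/Abdominal Sacrocolpopexy".

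Statistical Analysis begins "Given the descriptive nature of this study, limited statistical analysis will be performed" and then specifies proportions only. It sets out no summary of operative time or blood loss by support status, and no stratification or adjustment.

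**The concern.** Operative time and blood loss can plausibly differ between vaginal, abdominal, laparoscopic and robotic hysterectomy. If the route mix also differs between cases with and without apical support, a crude difference in time or blood loss will partly be a difference in route. Reported under an aim about surgeon characteristics, it would be read as a trait of the surgeons.

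The listed fields offer little protection. The type of apical support sometimes points to a route (a robotic or abdominal sacrocolpopexy, for example), but it is empty by definition in unsupported cases. The only partial proxy is therefore missing in the group that the aim describes. The list of concurrent procedures covers what accompanied the hysterectomy and does not clearly include its approach.

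Two things are at stake: how two of the five secondary-aim items are interpreted, and whether the study can say if omission is concentrated in one route. The second would be a directly usable finding for a practice review.

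**Working it through.** The plan has no figure of its own to reproduce here: no sample size, power, significance level or standard deviation is given. The check is a comparison of sections, followed by an illustration under stated assumptions.

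**Sections side by side**

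| Item | Where | Finding |
|---|---|---|
| Time and blood loss in the secondary aim | Purpose of Study | Yes |
| Route restricted by eligibility | Participants | No |
| Route on the data list | Data Collection | No |
| Partial proxy for route | Data Collection, type of apical support | Supported cases only |
| Stratification or adjustment | Statistical Analysis | None |
| Chart can be traced again | Data Collection; Privacy information | Yes: the data include "name, date of birth, age, race, parity, BMI" and date of surgery, and "identifying information will be retained in the original/source documents" |

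**Number of unsupported cases.** The Sample size section gives about 194 eligible cases. The hypothesis is fewer than 10% without support, so 194 × 0.10 = 19.4 is a ceiling under the hypothesis, not an expected count. If the full 250 requested charts were eligible, the ceiling would be 250 × 0.10 = 25.

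**Size of a route artefact, in minutes.** Artefact = (time difference between two routes) × (difference in route share between groups). Neither term is in the documents. Assuming 30 to 90 minutes between routes:

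- equal route share: 0 minutes;
- a 20-point difference in share: 30 × 0.20 = 6 to 90 × 0.20 = 18 minutes;
- a 40-point difference: 30 × 0.40 = 12 to 90 × 0.40 = 36 minutes.

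**Size relative to sampling error.** Take 19 unsupported and 194 − 19 = 175 supported cases. In SD units, SE = √(1/19 + 1/175) = 0.242. The artefact is b = (difference in share) × (route effect in SD). If someone applied a two-sided 5% normal test to the crude difference when there was no true surgeon difference, it would reject with probability 1 − Φ(1.96 − b/SE) + Φ(−1.96 − b/SE).

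| Difference in route share | Route effect 0.5 SD: b, rejection rate | Route effect 1.0 SD: b, rejection rate |
|---|---|---|
| 0 points | 0; 5% | 0; 5% |
| 20 points | 0.10; 7% | 0.20; 13% |
| 40 points | 0.20; 13% | 0.40; 38% |
| 60 points | 0.30; 24% | 0.60; 70% |

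The same table applies to operative time and to blood loss, since it is in SD units. It runs from no distortion to a severe one, and the documents do not say where in that range the study lies.

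**Operative time and the apical procedure.** Length of procedure includes the time spent on the suspension when one is done. A crude comparison therefore partly measures the omission itself, whatever the route mix.

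**The case against.** The strongest reply is that nothing formal depends on this. The study is descriptive, the analysis section plans no test or model for time or blood loss, and the primary proportion does not use route. Choice of route may itself be part of a surgeon's practice, so an unstratified profile is not wrong as description. All of that stands, and it limits the consequence. It does not remove the gap, because the aim still promises time and blood loss as surgeon characteristics and the listed fields give no means of reading them within route.

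Three stronger readings are tempting, and the documents support none of them.

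- A reader might infer that the omission cannot be put right later. Identifiers and date of surgery are abstracted and the source records are kept, so route can be re-abstracted, subject to any approval needed. The limit applies to the listed dataset only.
- A reader might infer that the comparisons are confounded. That needs route both to differ by support status and to affect time or blood loss. It is plausible, but the documents give no data on either.
- A reader might infer that, with about 19 unsupported cases, an artefact would dominate. The artefact does not depend on the number of cases, and a small group adds random error, which makes a fixed bias smaller relative to noise.

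It is also fair to say that the list may summarise a fuller abstraction form that is not shown, and that about 19 cases spread over four routes leaves roughly 5 per cell (19 / 4 = 4.75). The first cannot be settled from the documents. The second is a reason to collapse categories, not to leave route unrecorded.

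**Conclusion.** The point holds in a limited form. Route of hysterectomy is absent from the listed operative details, eligibility admits any route, and the secondary aim uses two outcomes that may depend on route. From the listed dataset those outcomes cannot be stratified by route, and clustering of omission by route cannot be shown.

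The size is unknown. The artefact is zero if route mix is equal in the two groups; the 6 to 36 minutes and the 7% to 70% rejection rates above rest wholly on assumed route effects and imbalances, with the rejection rates also taking the group sizes at the hypothesis ceiling. The primary result is unaffected and the gap can be repaired from the charts. This is a worthwhile, inexpensive improvement to a descriptive secondary aim, not a flaw that invalidates the study.

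**What to change.** 1. Under Data Collection, add to the operative details: route of hysterectomy (vaginal / abdominal / laparoscopic / robotic). If abstraction is complete, re-abstract this field from the retained charts, subject to any approval needed.
2. Under Statistical Analysis, add the proportion without apical support by route, with counts.
3. Show operative time and blood loss by route and support status as median and IQR, without testing. Collapse route (for example, vaginal versus other) where cells are small.
4. State that a crude difference between cases with and without support will not be presented as a surgeon characteristic, and that operative time includes the apical procedure itself. Stratifying by route does not remove that second effect.

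The cost is one extra field from operative records already under review, for at most 250 charts, and some small cells. It is higher if charts must be reopened. The protocol is dated 9/27/18, while its timetable has a January 2018 start and 2 + 2 + 3 + 8 = 15 weeks to the end of data collection. The documents do not say whether that timetable was kept.
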